*2. What is/are the research question(s)/specific aim(s)? Pose very specific questions that can be addressed within the proposed design of the study. Prioritize them in order of importance.*

The specific aim of the study is to determine whether the use of perioperative IV TXA, given prior to incision (concurrent with preoperative antibiotics) and then at wound closure, reduces the calculated total blood loss postoperatively in patients undergoing PAO when compared to a patients receiving placebo (normal saline). A 250 mL difference in blood loss will be considered a clinically important difference [18].

Secondary objectives of the study are to study whether the use of IV TXA reduces intraoperative cell saver utilization, transfusion of allogeneic blood, and hospital length-of-stay (LOS) compared to placebo use. We will also compare complications between study groups, including the incidence of clinically apparent deep vein thrombosis (DVT) and pulmonary embolism (PE), from postoperative day zero through 6 weeks postoperatively.

3. *What is/are the hypothesis(es)?*

**Hypothesis 1:** The use of IV TXA given prior to incision and at the time of wound closure will decrease the postoperative calculated total blood loss in patients undergoing PAO compared to patients receiving placebo.

**Hypothesis 2:** Patients receiving perioperative IV TXA will have lower intraoperative cell saver utilization, lower rate of allogeneic blood transfusion, shorter hospital LOS after PAO compared to patients receiving.

**Hypothesis 3:** There will be no difference in the rate of symptomatic venous thromboembolic events (VTE) (i.e., DVT and PE) in the 6 weeks after PAO surgery in patients who receive perioperative IV TXA compared to patients receiving placebo.

4. *Identify and define the primary outcome and when the outcome will be measured. If measuring change in post-operative function is the most important, that will be your primary outcome.*

Postoperative calculated total blood loss after PAO, determined from estimated blood volume [19], change in postoperative hemoglobin (preoperative hemoglobin – final inpatient hemoglobin), and transfused hemoglobin [20,21].

5. *Identify and define the secondary outcome(s) and when they will be measured (list additional goals one at a time with their corresponding outcomes).*

Secondary outcomes:

1. Intraoperative cell saver utilization: cumulative mL of reinfusion, measured at the end of the case intraoperatively

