**Data recorded from the operating room record will include:**

- Anesthetic used (e.g., regional, general, etc.)
- Operative times (minutes)
- Intraoperative transfusion requirements (units of blood)
- Use of cell saver intraoperatively (autotransfusion volume, mL)

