The randomization schedule will be generated by the HSS Epidemiology & Biostatistics Core with the randomization list provided to the investigators prior to initiation of patient recruitment. It will be a double-blind experiment with all parties, except the pharmacy, being blinded to the randomization schedule (surgeon, anesthesiologist, research assistant, and patient). Patient recruitment will continue until a total of 80 patients are enrolled.

*Treatment Arms:*

PAO will be performed as per the study surgeon's routine practice. In general, the operative extremity and hemipelvis will be prepped and draped in the usual sterile fashion. Prior to incision, the anesthesiologist, who will be blinded to the study group, will administer either 10 mg/kg, up to a maximum of 1 g, of IV TXA (diluted in 50 mL of normal saline, with a maximum concentration of 100 mg/mL) or 50 mL of normal saline prepared by the pharmacy. Only anesthesiologists agreeing to participate in the study will be paired with the study surgeons. A Smith-Petersen approach will be used, and standard surgical techniques for intraoperative hemostasis will be utilized.

Intraoperatively, a cell saver will be used, and the volume (mL) of autotransfusion will be recorded. The ischial, pubic, supra-acetabular, and retro-acetabular osteotomies will be performed, and the surgeon will then re-orient the acetabular fragment to achieve the desired correction. Cortical screws will then be placed for definitive fixation. After all hardware is placed, the wound will be thoroughly irrigated and suctioned. The anesthesiologist will administer either a second dose IV TXA as described above or a 50 mL bolus of normal saline, as prepared by the pharmacy, and the wound will be closed in layers. Routine, daily inpatient CBC data will be reviewed. Inpatient and office records will be accessed to help identify postoperative complications.

*Outcome Measures*

Primary outcome: Calculated total blood loss.

Secondary outcomes of interest: Postoperative allogeneic blood transfusion, and intraoperative cell saver utilization.

Calculated total blood loss will be determined from the difference between the preoperative hemoglobin and the lowest postoperative hemoglobin during the hospital stay (or the lowest postoperative hemoglobin prior to transfusion). Based on hemoglobin balance, the estimated blood loss will be calculated according to the formula by Nadler et al. [19]:

Hospital for Special Surgery

IRB# \_\_\_\_\_

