Form 1 -Clinical Research Proposal Form

$$\text{Estimated Blood Volume (EBV)} = (k_1 \times \text{Height}^3 \text{ (m)}) + (k_2 \times \text{Weight (kg)}) + k_3$$

For men,  $k_1 = 0.3669$ ,  $k_2 = 0.03219$ , and  $k_3 = 0.6041$

For women,  $k_1 = 0.3561$ ,  $k_2 = 0.03308$ , and  $k_3 = 0.1833$

Multiplying the EBV by the hematocrit (Hct) gives the red blood cell (RBC) volume. As such, a change in the RBC volume can be calculated from a change in the Hct level [20, 21]:

$$\text{Total RBC volume loss} = \text{EBV} \times (\text{Hct Preop} - \text{Hct Postop})$$

Transfusions (mean volume per unit, mL) can be taken into account by calculating the total blood loss:

$$\text{Total blood loss (L)} = \text{Total RBC volume loss} + (\text{No. of Units Transfused} \times 0.285) / (\text{Hct Preop} - \text{Hct Postop}) / 2$$

The rate of perioperative blood transfusions, both intraoperative and postoperative, will be documented for analysis.

The criteria for transfusion of blood products will be a hemoglobin level of  $< 8.0$  g/dL or a hemoglobin level of  $< 10.0$  g/dL with clinical signs of symptomatic anemia (e.g., chest pain that was deemed to be cardiac in origin, congestive heart failure, unexplained tachycardia, or hypotension unresponsive to fluid replacement). Blood will be administered 1 unit at a time, and the presence of symptoms or signs will be reassessed. Of note, the chart of the patient will clearly indicate him/her as a study patient.

VTE prophylaxis will be standardized, with each patient receiving 3 weeks of prophylaxis with 325 mg of oral aspirin twice daily. All patients will also receive a comprehensive, multidisciplinary approach to postoperative care with mechanical (sequential compressive device) prophylaxis in-house, early mobilization with physical therapy, medical optimization, and regional anesthesia, if appropriate.

**4. What is the long-term significance? - state the potential long-term benefits of the study, why it is important and its potential significance.**

The risk of excessive blood loss and blood transfusion in young, healthy patients after elective surgery is an event that can be reduced with blood conservation protocols, which can include pharmacological agents like TXA. If the use of IV TXA in the PAO patient population significantly reduces total perioperative blood loss, then it would provide an efficacious and inexpensive method for reducing postoperative morbidity after PAO.

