**D. SAMPLE SIZE AND DATA ANALYSIS**

If you are uncertain about how to calculate your sample size and determine appropriate data analysis, please contact the Epidemiology and Biostatistics Core at [[contact]](mailto:[contact]) for assistance in completing this section.

*If this is a case series based only on the patients available and only descriptive statistics will be obtained, state this in lieu of a sample size calculation. However, if you propose a case series, but plan hypothesis testing (e.g., the calculation of p-values using statistical tests) you need to estimate your*

**Sample Size – Support estimates with evidence from the literature or prior studies and perform an appropriate sample size calculation.**

Proposed analysis (e.g., student's t-test, ANOVA, chi-square, regression, etc.):

Outcome variables of interest are all continuous. Two-sample t-test and multivariate linear regression will be utilized if the data is normally distributed; otherwise Mann-Whitney U test (non-parametric equivalent to the two-sample t-test) will be utilized.

1. Alpha level: 0.05
2. Beta or power level: 0.82
3. Primary outcome variable estimate (mean +/- s.d. for continuous outcome, frequency/percentage for categorical variable):

The primary outcome will be the calculated total blood loss, summarized as mean +/- s.d. Based on historical data of patients that underwent PAO or PAO/Scope without IV TXA, the mean calculated blood loss was approximately 1296 mL with a standard deviation of 383.27 mL.

4. Number of groups being compared (use 1 for paired analysis within the same subjects):

Two groups will be compared: treatment arm (up to 1 g of IV TXA diluted in 50 mL of normal saline) versus those receiving placebo (50 mL of normal saline)

5. Effect size or change expected between groups: 250 mL difference in blood loss
6. Resulting number per group: 40 per group
7. Total sample size required: 80

**Data Analysis - describe how the primary outcome will be analyzed and what types of statistical calculations will be used. Do the same for each secondary outcome. Reiterate briefly the main analysis to be done, which groups, which variables, possible confounders. Address how possible confounders will be identified and handled in the analysis.**

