The primary outcome, calculated total blood loss, will be presented as mean +/- standard deviation and compared between the TXA and placebo arms with a two-sample t-test. Multiple linear regression will also be used to compare total blood loss volume between arms after adjustment for age, sex, BMI, and anesthesia type.

Calculated total blood loss will be determined from the difference between the preoperative hemoglobin and the lowest postoperative hemoglobin during the hospital stay (or the lowest

postoperative hemoglobin prior to transfusion). Based on hemoglobin balance, the estimated blood loss will be calculated according to the formula by Nadler et al. [19]:

$$\text{Estimated Blood Volume (EBV)} = (k_1 \times \text{Height}^3 \text{ (m)}) + (k_2 \times \text{Weight (kg)}) + k_3$$

For men,  $k_1 = 0.3669$ ,  $k_2 = 0.03219$ , and  $k_3 = 0.6041$

For women,  $k_1 = 0.3561$ ,  $k_2 = 0.03308$ , and  $k_3 = 0.1833$

Multiplying the EBV by the hematocrit (Hct) gives the red blood cell (RBC) volume. As such, a change in the RBC volume can be calculated from a change in the Hct level [20, 21]:

$$\text{Total RBC volume loss} = \text{EBV} \times (\text{Hct Preop} - \text{Hct Postop})$$

Transfusions (mean volume per unit, mL) can be taken into account by calculating the total blood loss:

$$\text{Total blood loss (L)} = \text{Total RBC volume loss} + (\text{No. of Units Transfused} \times 0.285) / (\text{Hct Preop} - \text{Hct Postop}) / 2$$

Continuous secondary outcomes (postoperative allogeneic blood transfusion, intraoperative cell saver utilization, and length of hospital stay) will be analyzed in the same manner as the primary outcome.

The incidence of complications will be reported as proportions and 95% confidence intervals.

All hypotheses will be evaluated with two-sided tests with statistical significance set at  $\alpha = 0.05$ .

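### The primary blood-loss formula has no term for red cells returned by the cell saver, so it measures something short of total loss and may understate the TXA difference

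*Combined protocol and SAP*

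**What the plan says.** Section A.4 defines the primary outcome from estimated blood volume, the change in hemoglobin, "and transfused hemoglobin [20,21". It does not say whether cell saver blood counts as transfused.

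Section C.3(g), Outcome Measures, and Section D, Data Analysis, print the same calculation. Red-cell loss is EBV times the fall in hematocrit. One transfusion term follows, introduced by "Transfusions (mean volume per unit, mL) can be taken into account by calculating the total blood loss": number of units times 0.285, divided by (Hct Preop - Hct Postop) / 2. No other term is present.

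On the cell saver, Section C.3(a) and the Treatment Arms text say "Intraoperatively, a cell saver will be used, and the volume (mL) of autotransfusion will be recorded". The operating-room data list has "Use of cell saver intraoperatively (autotransfusion volume, mL" as an item separate from units of blood transfused. Section A.5 makes the reinfused mL a secondary outcome, measured at the end of the case. Hypothesis 2 in Section A.3 expects that TXA patients "will have lower intraoperative cell saver utilization".

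**The concern.** A hemoglobin balance infers loss from the fall in red-cell mass, so any red cells given back before the postoperative sample must be added in. The plan does this for bank units but not for reinfused cells. Those cells raise the postoperative hematocrit and lower the computed loss.

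The omission matters for the comparison because the plan itself expects reinfusion to differ by arm. If more is returned on placebo, more loss goes uncounted there and the contrast shrinks. This affects the only primary outcome and the interim efficacy test, which uses the same variable. It also leaves open a choice, whether to count reinfusate, that should not be made after the data have been seen.

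**Working it through.** **1. The plan's own figure.** Inputs from Section D: "Alpha level: 0.05", two-sided; "Beta or power level: 0.82"; difference 250 mL; SD 383.27 mL; 40 per arm. Standardized difference = 250 / 383.27 = 0.652. The noncentral t distribution gives 82.1% power at 40 per arm, and 82% power needs 39.85, so 40 per arm. The stated design reproduces.

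**2. Could the formula already include reinfusate?** The transfusion term is a count of units times a mean volume per unit. Reinfusate is recorded in mL, as a separate item. Reinfusion is complete at the end of the case and every hemoglobin that the plan might use is postoperative, including the lowest value before transfusion. The returned cells are therefore in the measured value and absent from the formula.

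**3. One patient, by hemoglobin balance.** Assumed: woman, 1.65 m, 65 kg, Hct 0.40 falling to 0.28, 250 mL reinfused at Hct 0.55, no bank units.
- EBV = 0.3561 x 1.65^3 + 0.03308 x 65 + 0.1833 = 3.93 L.
- Red-cell loss = 3.93 x 0.12 = 0.472 L; mean Hct = 0.34.
- Without the returned cells: 0.472 / 0.34 = 1.39 L.
- With them: (0.472 + 0.250 x 0.55) / 0.34 = 0.6095 / 0.34 = 1.79 L.
- Uncounted: about 0.40 L.

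**4. The same patient, by the formula as printed.** The printed divisor is half the hematocrit fall, not the mean hematocrit, and it applies only to the transfusion term.
- Untransfused: the result is 0.472 L of red cells, never converted to blood. At an assumed product Hct of 0.45-0.65, each 100 mL reinfused hides 45-65 mL.
- One bank unit, with reinfusion: 0.472 + 0.285 / 0.12 / 2 = 1.66 L.
- One bank unit, had the cells not been returned: Hct would be 0.28 - 0.1375 / 3.93 = 0.245, a fall of 0.155, giving 0.609 + 0.285 / 0.155 / 2 = 1.53 L.

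Read literally, the direction reverses in this transfused patient. The under-count in step 3 belongs to the intended balance.

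**5. Between arms.** Let f be the share of a true 250 mL gross difference that is hidden. Apparent difference = 250 x (1 - f), with SD held at 383.27 mL.

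| f | Apparent difference | Power, 40 per arm | n per arm for 82% |
|---|---|---|---|
| 0 | 250 mL | 82.1% | 40 |
| 10% | 225 mL | 73.7% | 49 |
| 20% | 200 mL | 63.5% | 62 |
| 30% | 175 mL | 52.3% | 81 |

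In terms of volume, at an assumed product Hct of 0.5-0.6 and mean Hct of 0.34, a 25 mL arm difference in reinfusate hides 25 x 0.5 / 0.34 = 37 mL to 25 x 0.6 / 0.34 = 44 mL (power 69-66%). A 50 mL difference hides 74-88 mL (power 53-46%).

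**6. Cost of the added term in variance.** Assume reinfused volume has SD 100 mL and the Hct ratio is 0.55 / 0.35. The term's SD is 157 mL. If it is uncorrelated with net loss, total SD = sqrt(383.27^2 + 157^2) = 414 mL and power at 250 mL is 76%. At correlation 0.3 the SD is 456 mL and power is 68%.

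**The case against.** The strongest reply is that the planning figures may already be on the net scale. The historical 1296 mL and SD 383.27 mL are calculated blood loss from the same surgeon's cases. If they came from a calculation without reinfusate, and 250 mL is read on that scale, planned power is unchanged and the fault is one of naming. The documents do not settle this, so the reply stands as a condition on every power figure above.

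Second, a reader might infer that each 100 mL arm difference in reinfusate hides 118-203 mL of loss (product Hct 0.45-0.65 over patient Hct 0.32-0.38). That presumes a mean-hematocrit divisor which the plan does not print. As step 4 shows, the literal formula gives smaller figures in untransfused patients and can reverse in transfused ones, and 33.3% of the historical patients were transfused.

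Third, Hypothesis 2 is an expectation. If TXA acts mainly after closure, reinfusion may be similar in the two arms and little would be hidden.

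Fourth, attenuation is conservative for a superiority claim, and a difference in reinfusion would show in the secondary outcome. Both are true, but neither makes the primary estimate one of total loss.

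**Conclusion.** The omission is certain from the text: recorded reinfusate does not enter an outcome named total blood loss. The direction, toward understating a TXA benefit, follows if the hemoglobin-balance intent governs and if reinfusion is lower on TXA. The size is not known. The fall from 82.1% to 74-52% power illustrates 10-30% of a 250 mL gross difference being hidden with the SD unchanged, and 82% stands if the 250 mL and the historical figures are both net of reinfusion.

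A reader might go further and conclude that the trial is biased toward no effect by a known amount, or is underpowered. The documents support neither, because they give no reinfusion volume, product hematocrit or scale for the planning figures.

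**What to change.** Make these changes in both places where the formula is printed (Section C.3(g), Outcome Measures, and Section D, Data Analysis), before any unblinded look, including the interim analysis.

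1. Correct the conversion first: divide the whole red-cell balance by the mean of preoperative and postoperative hematocrit, not by (Hct Preop - Hct Postop) / 2. Order matters. In the example patient, the new term put through the printed divisor would be 0.1375 / 0.12 / 2 = 0.57 L, or 0.1375 / 0.06 = 2.29 L, against the intended 0.40 L.
2. Add cell saver reinfused volume (L) times a prespecified product hematocrit to the balance, beside the allogeneic term.
3. Repeat the primary analysis without the term, and over a stated range of product hematocrit such as 0.45-0.65.
4. Recompute the historical mean and SD, and the stated power, on the same scale wherever reinfusion volumes are on file.

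The cost is a corrected divisor, one term and one constant, with no new data from trial patients. The product hematocrit remains an assumption, which step 3 covers only over the stated range. The added term may also raise the SD and lower the stated power, to 76-68% under the assumptions in step 6 of the working.

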**A. SPECIFIC AIMS OR RESEARCH QUESTIONS - answer each question individually.**

*1. What is the condition or intervention to be studied?*

Periacetabular osteotomy (PAO) is an elective reorientation surgery for the hip joint, typically for the treatment of hip dysplasia in young, otherwise healthy patients, which requires multiple pelvic osteotomies around the acetabulum [1]; a major source of its perioperative morbidity is blood loss [2]. The principal cause of postoperative blood loss after PAO is surgical trauma, with secondary activation of both the coagulation cascade and local fibrinolysis [3]. Tranexamic acid (TXA) is a synthetic derivative of the amino acid lysine that acts as competitive inhibitor of plasminogen activation, interfering with fibrinolysis [4]. Multiple studies and meta-analyses have shown that intravenous (IV) of TXA reduces postoperative bleeding and the need for transfusion after orthopedic surgery, including total joint arthroplasty, with no demonstrable change in the risk for postoperative complications, including venous thromboembolic events (VTE) [5-10]. However, there is no prospective data regarding TXA use for PAO, and, in our experience, PAO surgeons question and argue the use and disuse of TXA for this procedure.

In the PAO literature, allogeneic transfusion rates are as high as 58% [11], and blood loss can range to nearly 4 L [2, 11-17]. If autologous blood and intraoperative cell saver are considered along with allogeneic transfusions, the risk of perioperative transfusion can be as high as 94% [2].

Retrospectively, we reviewed 93 PAO cases performed by the principle investigator of this study. The average calculated blood loss was  $1.30 \pm 0.38$  L (range, 0.32 L – 2.65 L), and 33.3% of patients required at least one transfusion of allogeneic blood postoperatively. There has been one retrospective study examining the effect of IV TXA on blood loss and transfusion after PAO that showed that IV TXA may reduce total blood loss by 30.8% ( $p=0.001$ ) and transfusion rate by 58.6% ( $p=0.013$ )[11].

The goal of this randomized controlled, double-blinded trial is to assess the efficacy of IV TXA in reducing calculated total blood loss in patients undergoing PAO. Our specific objectives included analysis of (1) calculated total blood loss (primary outcome), (2) intraoperative cell saver utilization (secondary outcome), and (3) postoperative allogeneic blood transfusion (secondary outcome).

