**Data recorded from the electronic medical record will include:**

- Date of surgery
- Patient age at the time of surgery
- Patient gender
- Patient height (cm) and weight (kg) at time of admission

- Transfusion requirement during inpatient stay (units required)
- Postoperative day and time of discharge
- Preoperative CBC data and coagulation study data
- Postoperative hemoglobin on all inpatient days postoperatively (g/dL)
- Chart review of progress notes for evidence of clinically significant VTE
- Chart review of progress notes for evidence of reoperation, hematoma, seroma, or postoperative infection

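### The primary blood-loss outcome has conflicting postoperative hemoglobin definitions, and the transfused units it adds are not tied to the draw

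*Combined protocol and SAP*

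**What the plan says.** All references are to the combined protocol and SAP.

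- **Section A.4** defines the primary outcome from estimated blood volume, the preoperative hemoglobin minus the "final inpatient hemoglobin), and transfused hemoglobin".
- **Section C.3(g), Outcome Measures**, uses a different postoperative value: "the lowest postoperative hemoglobin during the hospital stay (or the lowest postoperative hemoglobin prior to transfusion".
- **Section D, Data Analysis**, repeats this: it starts from "the difference between the preoperative hemoglobin and the lowest postoperative hemoglobin during the hospital stay" and offers the same parenthetical alternative. Neither place says when the alternative applies.
- **The formula**, printed in both C.3(g) and D, is introduced by "Transfusions (mean volume per unit, mL) can be taken into account by calculating the total blood loss". Its transfusion term is the number of units times 0.285, divided by the Hct difference and then by 2. It sets no time window for the units.
- **Section C.3(b)** lists "Postoperative hemoglobin on all inpatient days postoperatively (g/dL" and "Transfusion requirement during inpatient stay (units required". The operating room record adds intraoperative units and the cell-saver volume in mL. No time of transfusion is listed. The attached data collection sheet is not available to me and may hold one.
- **Section D** also plans one interim efficacy test on calculated blood loss when outcome data are in for half the patients.

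**The concern.** Final, lowest and lowest pre-transfusion hemoglobin are three different numbers in many patients, and the plan allows each of them somewhere. With daily values on file, the definition could be settled after data have been seen, including at the interim look.

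The units make this worse. A unit given before the draw has raised the measured Hct, so adding it back is right. A unit given after the draw has not. Adding it to a low pre-transfusion Hct can count red-cell loss that never occurred. Transfusion is common in this setting (section A.1: "33.3% of patients required at least one transfusion of allogeneic blood postoperatively"), and Hypothesis 2 expects it to differ by arm. The choice could therefore alter the estimated difference in mL as well as add noise.

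**Working it through.** **1. The plan's own figure.** Inputs from sections C.2(c) and D: 40 per arm, difference 250 mL, SD 383.27 mL, two-sided alpha 0.05. Noncentrality = 250 / (383.27 × √(2/40)) = 250 / 85.70 = 2.917 on 78 degrees of freedom. Power is 82.1%, so the stated 82% reproduces. The plan does not say which hemoglobin draw produced that SD.

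**2. Red-cell balance.** Red-cell loss up to a draw = EBV × (Hct preop − Hct at draw) + red cells transfused before that draw. The final draw with all earlier units closes this balance. A pre-transfusion draw closes it only if later units are left out. Counting one later unit overstates loss up to that draw by as much as 0.285 L, treating the plan's constant as red cells. As a measure of loss over the whole stay, the excess falls to zero if a full unit's red cells are lost afterwards.

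**3. Illustration.** Body size and Hct values are my assumptions; Hct is taken from the same sample as the hemoglobin. Woman, 1.65 m, 65 kg: EBV = 0.3561 × 1.65³ + 0.03308 × 65 + 0.1833 = 3.933 L. Preoperative Hct 39%, 23% before one postoperative unit, final Hct 25% or 26%. The unit is counted in every row.

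| Draw | Red-cell loss, L | Total as printed, L | Total with mean-Hct divisor, L |
|---|---|---|---|
| 23%, pre-transfusion | 3.933 × 0.16 + 0.285 = 0.914 | 0.629 + 0.285/0.16/2 = 1.520 | 0.914/0.31 = 2.949 |
| 25%, final | 3.933 × 0.14 + 0.285 = 0.836 | 0.551 + 0.285/0.14/2 = 1.568 | 0.836/0.32 = 2.611 |
| 26%, final | 3.933 × 0.13 + 0.285 = 0.796 | 0.511 + 0.285/0.13/2 = 1.607 | 0.796/0.325 = 2.450 |

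Pre-transfusion minus final:
- red-cell loss: +0.08 to +0.12 L
- printed total: −0.05 to −0.09 L
- mean-Hct total: +0.34 to +0.50 L

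For EBV from 3.16 L (1.55 m, 50 kg) to 4.74 L (1.75 m, 80 kg), the printed gap runs from −0.03 to −0.11 L. The sign flips because the printed divisor is the Hct difference, which shrinks as the final Hct rises. The mean-Hct divisor is not in the plan.

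**4. Counting the later unit or not.** At the 23% draw the printed total is 0.629 L without the unit and 1.520 L with it, a change of 0.285/0.16/2 = 0.89 L.

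**5. Untransfused patients.** The printed formula reduces to EBV × Hct difference, so each Hct point between lowest and final moves the result by 3.933 × 0.01 = 0.04 L.

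**6. Patients affected and the arm difference.** Section A.1 gives a site transfusion rate of 33.3% and, from one retrospective study, a 58.6% relative reduction. If both apply, the TXA rate is 0.333 × (1 − 0.586) = 0.138, and 40 × (0.333 + 0.138) ≈ 19 of 80 patients are transfused. With no reduction it is 80 × 0.333 ≈ 27. If each transfused patient has one unit, given after the draw, the rate difference of 0.333 × 0.586 = 0.195 moves the arm difference as follows (pre-transfusion versus final draw):
- red-cell loss: larger by 0.195 × 0.079 to 0.195 × 0.118 = 0.015 to 0.023 L
- printed total: smaller by 0.195 × 0.049 to 0.195 × 0.088 = 0.01 to 0.02 L

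**7. Plausibility of the mean-Hct litres.** Section A.1 reports 1.30 ± 0.38 L with one third transfused. Even if all variation lay between transfused and untransfused patients, an SD of 0.383 L would cap the transfused mean at 1.30 + 0.383 × √2 = 1.84 L. Totals of 2.45 to 2.95 L are therefore not typical of this site.

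**The case against.** The strongest reply is that the two operational sections agree with each other word for word and carry the formula. On that view A.4 is a one-sentence outlier, and because daily hemoglobin is collected, any definition stays computable. This is fair as far as it goes and makes the repair largely editorial. It does not settle the endpoint: A.4 is where the form asks for the primary outcome to be defined, the operational text itself offers two draws, and neither place ties units to a draw.

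A second reply concerns size. The arm-level shift rests on assumed body size, Hct values and unit timing, and on an outside study's relative reduction. The figure of one unit per transfused patient is also an assumption; that study's means (section B.2: 1.02 units at a 58% rate, 0.28 at 24%) imply about 1.8 and 1.2. This stands, and the arm-level figures are illustrations only.

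A reader might infer that the plan overstates blood loss in transfused patients and so favours TXA. The documents do not support that for total loss. Compared with the final draw, the printed formula moves the other way; the overstatement appears only on the red-cell scale or with a divisor that the plan does not print. Compared with leaving the later unit out, the printed formula does give a larger value.

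**Conclusion.** The point stands as a contradiction in current text about the only primary outcome, together with a missing rule on which units count. That much is certain. The size and direction of the effect are not.

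Under the stated assumptions, the choice of draw moves one transfused patient's printed total by 0.05 to 0.09 L. Counting or omitting one later unit moves it by about 0.89 L, against a 250 mL target. The 0.34 to 0.50 L gap with a mean-Hct divisor should not be read as an expected effect.

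If TXA has no effect, no arm difference is expected from this, only added noise. If TXA changes transfusion, the estimated difference can be distorted in a direction that depends on the formula. A reader might also infer that the trial is underpowered or that the SD is wrong. Neither is shown: the power reproduces, and the definition behind the SD is simply not stated. This should be fixed before the interim look, because that test uses this variable.

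**What to change.** Before the interim look, reconcile A.4, C.3(g) and D, including both printings of the formula, to one postoperative draw for all patients. Count only units, intraoperative and postoperative, given before that draw. Either choice is open to the sponsor:

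- **Final inpatient value.** All earlier units count. Add a sensitivity analysis at a fixed postoperative day, because the final draw follows discharge and Hypothesis 2 expects length of stay to differ by arm.
- **Lowest value before postoperative transfusion** (lowest in-hospital value if none is given). Later units are excluded, and the plan states that bleeding after that draw is not measured.

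Record each unit's timing relative to the draw, if the attached sheet does not already do so. Settle this together with the formula's divisor, which is a separate defect. Confirm which definition gave the 383.27 mL SD; if it differs from the one chosen, recompute the SD from the historical charts and restate the power.

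As a separate clarification, state whether cell-saver reinfusion counts as transfused hemoglobin: A.4 leaves this open, and the formula counts units only.

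The cost is wording, possibly one data field, and one sensitivity analysis if the final value is chosen. Daily hemoglobin, units and cell-saver volume are already collected.
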